6.5.2.2 Post-Scan Testing

Device Assessment and Programming

Following the MRI Scan, remove the subject from the MRI bore. Interrogate the ICD. Disable the MRI Settings. **Note: MRI settings must be disabled to ensure that tachyarrhythmia therapy is turned back on.** Obtain the following for the Durata or Optisure lead:

- In-clinic bipolar capture threshold at a pulse width of 0.5 ms. Either the manual decrement or automatic (in-clinic, programmer-based) method may be used to obtain the capture threshold.
- In-clinic bipolar sensing amplitude. Either the incremental or the automatic (in-clinic, programmer based) method may be used to obtain the sensing threshold.
- In clinic bipolar lead impedance
- In-clinic HVLI impedance

NOTE: RV capture thresholds are not required to be obtained if a high ventricular rate is present. If available, sites should use the automatically obtained pacing capture threshold from the most recent archival data as a substitute for the in clinic capture threshold. RV sensing measurements are not required if the subject's intrinsic rate is established to be ≤ 30 beats per minute.

Reporting of MRI Scan-Related Adverse Device Effects

An ADE or SADE related to the following should be reported as soon as possible, but no later than 10 working days, to St. Jude Medical: clotting, pulmonary embolism, or heating of the device pocket during the MRI scan. These events are likely to be associated with symptoms occurring during or immediately following the MRI scan and may manifest as chest pain, shortness of breath, or changes in vital signs during or immediately following the MRI scan.

To ensure all ADEs or SADEs related to or caused by the MRI scan are appropriately captured, before starting the scan, verbally instruct the subject to report symptoms of chest pain, shortness of breath or pocket discomfort that he/she experiences while being scanned or immediately after exiting the scanner. Note changes in vital signs such as changes in heart rate, room air blood oxygen saturation, and/or respiration rate that occur during the MRI scan that may suggest an ADE or SADE has occurred due to clotting, pulmonary embolus or related to lead tip or device pocket heating.

Clinical Investigational Plan

If symptoms during or immediately after the MRI scan suggest that an ADE or SADE has occurred due to clotting, pulmonary embolus or related to lead tip or device pocket heating, test to assess possible causes. Diagnostic testing may be performed in any order deemed appropriate by the investigator; if any test was not performed, provide medical justification for not performing that test:

- (1) A 12-lead EKG
- (2) A 2-view chest X-ray (PA and Lateral).
- (3) Room air blood oxygen saturation
- (4) A transthoracic echocardiogram.

If the subject reports pocket discomfort, ask the subject for additional descriptive information and determine if the pocket is discolored or warm to the touch. EKG, chest x-ray, room air blood oxygen saturation, or transthoracic echocardiogram testing are not required to be performed for symptoms related to device pocket heating.

Sites should report an ADE or SADE if the subject experiences a significant rise in pacing threshold ([contact] or greater) from pre-MRI scan to one month post-MRI scan.

6.5.2.3 Data Submission

Once required testing has been performed, complete and submit the appropriate forms to St. Jude Medical. Refer to Table 5: Study Procedures and Data Collection

Export the study MRI scan onto a CD, or other form of electronic media in DICOM format, and send to St. Jude Medical. Upload post MRI scan device session records through the EDC study portal. It is recommended that the following device printouts and measurements be maintained at the site.

- FastPath Summary
- Test Results with Freezes, Include Battery & Leads
- Wrap-up Overview with full parameters
- Upload device session record

6.5.3 One (1) Month Post Scan Visit

6.5.3.1 Testing

Interrogate the ICD and obtain electrical measurements for the Durata or Optisure lead.

Clinical Investigational Plan

- In-clinic bipolar capture threshold at a pulse width of 0.5 ms. Either the manual decrement or automatic (in-clinic, programmer based) method may be used to obtain the capture threshold. If a significant rise in pacing threshold ([contact] or greater) from pre-MRI scan to one month post MRI scan has occurred, then complete an AE form.
- In-clinic bipolar sensing amplitude. Either the incremental or the automatic (in-clinic, programmer based) method may be used to obtain the sensing threshold.
- In-clinic Bipolar lead pacing impedance
- In-clinic HVLI impedance

Evaluate the subject for ADE, SADE, and UADE (for US sites) or USADE (for OUS sites) and submit an AE CRF CRF if applicable. Note if any spontaneous VT/VF episodes occurred on the Follow up CRF.

NOTE: RV capture thresholds are not required to be obtained if a high ventricular rate (e.g. 110bpm) is present. If available, sites should use the automatically obtained pacing capture threshold from the most recent archival data as a substitute for the in clinic capture threshold. RV sensing measurements are not required if the subject's intrinsic rate is established to be ≤ 30 beats per minute.

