
 • Lead electrode heating and tissue damage resulting in loss of sensing or capture or both • Lead heating resulting in thrombus formation or embolism • Device heating resulting in tissue damage in the implant pocket or subject discomfort or both • Induced currents on leads resulting in continuous capture, VT/VF, hemodynamic collapse, or all three • Damage to the device or leads causing: 
 a. the system to fail to detect or treat irregular heartbeats b. the system to treat the subject’s condition incorrectly • Damage to the functionality or mechanical integrity of the device resulting in the inability of the device to communicate with the programmer • Movement or vibration of the device or leads • Lead dislodgment • Competitive pacing and potential for VT/VF induction due to ambulatory asynchronous pacing in MRI mode • Pulmonary Embolism 	
These risks are mitigated through the selection of investigators who are qualified by training and/or experience to evaluate and treat subjects implanted with an ICD system.
 
In addition, study investigators will be trained on the study protocol to ensure the proper procedures are followed to assure subject safety during the study MRI scan. This includes continuous monitoring of the subject using pulse oximetry, ECG and verbal communication during the scan.
 
Advanced Cardiac Life Support (ACLS) procedures will be in place to address situations where a life threatening arrhythmia and/or hemodynamic collapse occurs. The programmer will be used outside the American College of Radiology (ACR) defined Zone 4 magnet room. If the subject’s hemodynamic function is compromised during the MRI scan, the MRI scan will be stopped, and proper measures will be taken to restore the subject’s hemodynamic function.

Potential ICD Related Events	

 • Refer to the Ellipse user’s manual for a full list of potential adverse events 	
The Ellipse VR ICD is a market-released ICD. The adverse events associated with this ICD are the same as those associated with other market-released ICDs.
 
These risks are mitigated through the

Clinical Investigational Plan

Event	Mitigation
	selection of investigators who are qualified by training and/or experience to evaluate and treat subjects implanted with an ICD.
Potential Lead Related Events	

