4.5.1 Inclusion Criteria

1. Are implanted with the Durata or Optisure lead for at least 60 days (can include patients with Durata or Optisure lead for ≥ 60 days OR patients with a new Ellipse VR ICD and/or Durata/Optisure lead implanted for at least 60 days)
2. Are implanted with an Ellipse VR ICD pectorally
3. Be willing to undergo an elective MRI scan without sedation
NOTE: Antianxiety agents (e.g. minor tranquilizers, etc.) may be used as long as the patient can communicate with site personnel during the MRI scan
4. Capture threshold is stable at $\leq [contact]$
5. Ventricular sensing is measurable (patient has underlying rhythm $> 30bpm$) and the sensing amplitude is $\geq 4mV$
6. Be able to provide informed consent for study participation (legal guardian or legally authorized representative is NOT acceptable)
7. Be willing and able to comply with the prescribed follow-up tests and procedures
8. Is not contraindicated for an MRI scan (per the MRI Screening Form)

Subjects are not eligible for clinical study participation if they meet any of the following exclusion criteria:

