- In-clinic bipolar sensing amplitude. Either the incremental or the automatic (in-clinic, programmer based) method may be used to obtain the sensing threshold. **Note: If the ventricular sensing is not measurable (patient has underlying rhythm < 30bpm) and the sensing amplitude is < 4mV, then the patient does not meet inclusion criteria.**
- In-clinic bipolar pacing and high voltage lead impedance

NOTE: RV capture thresholds are not required to be obtained if a high ventricular rate is present (e.g. 110bpm). If available, sites should use the automatically obtained pacing capture threshold from the most recent archival data as a substitute for the in clinic capture threshold. RV sensing measurements are not required if the subject's intrinsic rate has been established to be ≤ 30 beats per minute.

If the device testing results do not meet the MRI conditions for scanning per the MRI Procedure manual (also see below), or the patient's sensing threshold is not measurable or the sensing threshold is less than 4mV, the physician may choose to reschedule the subject to return for re-testing. The subject's 1 Month Post MRI Scan Visit will need to be rescheduled to correspond with the MRI Scan Visit where the MRI scan was completed.

Review the MRI checklist on the programmer. Verify the following conditions before saving the MRI Setting.

- Bipolar capture thresholds are stable at $\leq [contact]$ ms
- Bipolar pacing lead impedance is within range, i.e. ≥ 200 and ≤ 2000 ohms
- HVLI is within range, i.e. ≥ 20 and ≤ 200 ohms
- No additional hardware (adaptors, extenders, or abandoned leads)

Save the MRI Setting after the MRI Checklist has been reviewed, using the parameters listed in Table 6: MRI Parameters. Perform all other applicable tests and procedures.

Clinical Investigational Plan

Table 6: MRI Parameters

Parameters	Selectable Options	Nominal Values
MRI Mode*	VOO Pacing Off	Pacing off
MRI Base Rate	30-100 bpm, in steps of 5 bpm	n/a
MRI RV Pulse Configuration	Bipolar	n/a
MRI RV Pulse Amplitude	5.0 V, 7.5 V	n/a
MRI RV Pulse Width	1.0 msec	n/a
Tachy settings	Disabled	Disabled

***Note:** When MRI Settings are enabled, sensing is disabled. Determine whether or not the subject requires pacing support during the MRI scan. When pacing support is needed, set the MRI Mode to the asynchronous pacing mode (VOO). When pacing support is not needed, set the MRI Mode to Pacing Off.

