The hypothesis will be tested at the 2.5% significance level. The null hypothesis will be rejected if the 97.5% lower confidence bound for p_{E1} is greater than 90%. The 97.5% lower confidence bound will be calculated by the exact (Clopper-Pearson) method for binomial probabilities

Clinical Investigational Plan

12.1.3 Primary Efficacy Endpoint #2 (Change in Sensing Threshold for Durata and Optisure (RV) leads)

The primary efficacy endpoint #2 is the proportion of Durata or Optisure (RV) leads implanted with the Ellipse VR ICD with sensing amplitude decrease of $\leq 50\%$ from pre-MRI scan testing to 1 month post-MRI scan.

Hypothesis

Success is defined as ventricular sensing amplitude decrease of $\leq 50\%$ from pre-MRI scan testing to 1 month post-MRI scan. The hypothesis is formally expressed as:

$$H_0: p_{E2} \leq 87\%$$

$$H_a: p_{E2} > 87\%$$

where p_{E2} is the probability of success.

Analysis

The primary analysis will be conducted on subjects who meet all of the following criteria:

- Implanted with the Durata or Optisure RV lead and Ellipse VR ICD
- Sign informed consent
- Meet the MRI Conditions of Use
- Undergo a Study MRI scan
- Have MRI visit data for RV sensing threshold
- Have 1 month post-MRI scan visit data for RV sensing threshold
- Have not undergone any VR ICD lead repositioning or replacement since the MRI scan up to 1 month post-MRI scan
- Have an intrinsic heart rate ≥ 30 beats per minute at the time of ventricular capture threshold measurements

The null hypothesis will be tested at the 2.5% significance level. The null hypothesis will be rejected if the 97.5% lower confidence bound for p_{E2} is greater than 87%. The 97.5% lower confidence bound will be calculated by the exact (Clopper-Pearson) method for binomial probabilities.

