12.2 Sample size

12.2.1 Sample size for primary safety endpoint

In the St. Jude Medical Accent MRI pacemaker IDE study, the results of which were submitted in PMA 60067410/A, and another manufacturer's study involving an MRI conditional pacemaker, the complication-free rate was observed to be 100%.^{16,14}

Therefore, the sample size is calculated under the conservative assumption of

Clinical Investigational Plan

complication-free rate of 97%. Under this assumption, a sample size of 141 subjects will provide 90% power to reject the null hypothesis at a 2.5% significance level. The sample size was calculated using the exact binomial method in SAS® v9.4.

12.2.2 Sample size for primary efficacy endpoint #1 (Change in capture threshold for Durata or Optisure (RV) lead)

In the St. Jude Medical Accent MRI pacemaker IDE study, the results of which were submitted in PMA 60067410/A, the proportion of leads with an increase in threshold ≤ 0.5 volts from pre-MRI scan testing to 1-Month after the MRI scan was 100%.^{1,2}. Therefore, the sample size is calculated under the conservative assumption of 98% for the endpoint. Under this assumption, a sample size of 85 subjects will provide 80% power to reject the null hypothesis at a 2.5% significance level. The sample size was calculated using the exact binomial method in SAS® v9.4.

12.2.3 Sample size for primary efficacy endpoint #2 (Change in sensing threshold in Durata or Optisure (RV) lead)

In the St. Jude Medical Accent MRI pacemaker IDE study, the results of which were submitted in PMA 60067410/A, the proportion of leads with ‘ventricular sensing amplitude decrease of $\leq 50\%$ from pre-MRI scan testing to 1-Month after the MRI scan,’ was approximately 97%. Therefore, the sample size is calculated under the conservative assumption of 95% success rate for the ventricular sensing threshold endpoint. Under this assumption, a sample size of 118 subjects will provide 80% power to reject the null hypothesis at a 2.5% significance level. The sample size was calculated using the exact binomial method in SAS® v9.4.

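### A lead recorded as not measurable at 1 month can leave the sensing endpoint (E2) instead of counting as a failure

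*Combined protocol and SAP*

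**What the plan says.** - **Entry.** Inclusion criterion 5 (section 4.5.1) begins "Ventricular sensing is measurable (patient has underlying rhythm" above 30 bpm, and also asks for an amplitude of at least 4 mV. Section 6.5.1.1 re-checks this before the scan with a note that starts "If the ventricular sensing is not measurable (patient has underlying rhythm < 30bpm". Later in the same section, sensing that cannot be measured and sensing below 4 mV are listed as alternatives, either of which allows re-testing.
- **1-month test.** Section 6.5.3.1 asks for an in-clinic bipolar sensing amplitude, but adds: "RV sensing measurements are not required if the subject's intrinsic rate is established to be ≤ 30 beats per minute". Sections 6.5.1.1 and 6.5.2.2 and the footnotes to Tables 1 and 5 carry the same waiver. None says how the rate is to be established.
- **Analysis set.** Section 12.1.3 defines success as a fall in amplitude of no more than 50% from before the scan to 1 month. Among its criteria is "Have 1 month post-MRI scan visit data for RV sensing threshold". Another is an intrinsic rate of 30 bpm or more when the capture threshold was measured; the visit is not named.
- **Decision rule.** "The null hypothesis will be rejected if the 97.5% lower confidence bound for p_{E2} is greater than 87"%, by the exact Clopper-Pearson method.
- **Hazard.** Table 2 lists among the potential MRI effects: "Lead electrode heating and tissue damage resulting in loss of sensing or capture or both".
- **Missing data and exclusions.** Sections 12.8 to 12.10 refer to a separate SAP, whose text is not in the supplied document.

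**The concern.** A percentage fall needs a number at both visits. A subject who attends the 1-month visit but has no sensing value there falls outside the E2 set. Nothing in the supplied text says that an R-wave which cannot be measured is entered as 0 mV or scored as a failure.

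An eligible subject had a rhythm above 30 bpm and at least 4 mV on the day of the scan. For that subject, a missing value at 1 month, or a rate of 30 bpm or less, is something that arose after the scan. If the reason is that the lead no longer senses, the exclusion depends on the outcome: a 55% fall counts as a failure, while a complete loss recorded as not measurable counts as nothing. The error runs in one direction, towards passing, and concerns a hazard that the plan itself names.

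The rate criterion adds to this. It is tied to capture testing although the endpoint is sensing. The cut-offs also do not meet: above 30 bpm at entry, 30 or below for the waiver, 30 or above for the analysis set. A subject at exactly 30 bpm is excused from the test yet satisfies the rate criterion of the analysis set.

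**Working it through.** **Inputs.** From section 12.1.3: goal 87%, one-sided 2.5%, exact lower bound. From section 12.2.3: "the sample size is calculated under the conservative assumption of 95% success rate for the ventricular sensing threshold endpoint", 118 subjects, 80% power, and about 97% observed in the earlier pacemaker study. From section 12.2.5: data freeze at 141 subjects with the 1-month visit. The number of leads recorded as not measurable at 1 month is not given.

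**1. The plan's own figure.** At n = 118 the exact rule allows at most 8 failures: 110/118 has a lower bound of 87.08%, and 109/118 has 86.01%. The actual level is P(X ≤ 8 | 118, 0.13) = 0.0237 and the power is P(X ≤ 8 | 118, 0.05) = 0.863. From n = 118 upwards the power stays at or above 80%, so the stated 118 reproduces.

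**2. The rule at 141.** At most 10 failures are allowed: 131/141 has a lower bound of 87.34% (pass), and 130/141 has 86.47% (fail). If the true success rate is exactly 87%, the chance of passing is P(X ≤ 10 | 141, 0.13) = 1.9%.

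**3. Dropping k true failures from 141 attendees.** Each row shows the largest number of true failures that still passes.

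| k dropped | Analysed without them | Lower bound | Same data, all counted | Lower bound |
|---|---|---|---|---|
| 0 | 131/141 | 87.34%, pass | 131/141 | 87.34%, pass |
| 1 | 130/140 | 87.26%, pass | 130/141 | 86.47%, fail |
| 2 | 129/139 | 87.17%, pass | 129/141 | 85.61%, fail |
| 3 | 128/138 | 87.08%, pass | 128/141 | 84.75%, fail |

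At n = 118 one dropped failure does not change the result, because 109/117 has a lower bound of 86.97% and fails. Two do: 109/116 passes (87.96%), while 109/118 fails (86.01%).

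**4. How often one lead decides.** With one dropped failure at 141, ten or fewer true failures pass either way and twelve or more fail either way (129/140 has a lower bound of 86.38%). Only exactly 11 matters, with probability C(141,11) × p^11 × (1−p)^130 for a true failure rate p:
- p = 0.05: 4.6%
- p = 0.03: 0.25%

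These are ceilings for the one-lead case, because one of the 11 failures must also be the one that is dropped.

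**5. Effect on the false-pass chance (assumed shares).** Let the true success rate be 87% with everyone counted, and let a share q of all subjects be failures that are dropped. The number dropped is binomial(141, q). Among those analysed the failure rate is (0.13 − q)/(1 − q), and the exact rule is applied to the reduced n.

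| q | Expected number dropped (141q) | Chance of passing |
|---|---|---|
| 0 | 0 | 1.9% |
| 1% | 1.41 | 4.0% |
| 2% | 2.82 | 7.0% |
| 3% | 4.23 | 11.5% |

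The nominal level is 2.5%. The values of q are illustrations only; nothing in the documents supports a particular one.

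**The case against.** The strongest answer is that the waiver concerns the heart, not the lead. A reader might infer that section 6.5.3.1 excuses an absent R-wave. It does not: its trigger is an intrinsic rate of 30 bpm or less. A subject with a faster rhythm must still be tested, and a value near 0 mV is a fall of more than 50%, so it already fails E2. This stands. What it leaves open is a result entered as not measurable instead of as a number, or a rate judged low because the lead does not sense.

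A reader might also infer that the plan treats unmeasurable sensing and a slow rhythm as the same thing, because it pairs them in parentheses at entry. The milder reading is that a usable rhythm is needed to measure sensing at all. The pairing makes confusion possible but does not prescribe it.

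A third tempting inference is that every waiver at 1 month marks a change caused by the scan. The documents do not support that. The same waiver appears before the scan, Table 7 keeps scanned subjects who turn out not to be eligible, and a slow rate may have nothing to do with the lead.

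Other routes can reveal a loss. Session records are uploaded at 1 month, the arrhythmia committee reviews undersensing in flagged episodes, and a complication needing invasive intervention can count in the safety endpoint if it is adjudicated as MRI-related. These help detection, but none puts the subject back into E2. Finally, the separate SAP may hold a scoring rule, so its absence cannot be asserted. The criteria in section 12.1.3 are nevertheless explicit and, read alone, exclude these subjects.

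**Conclusion.** The point holds in a limited form. As written, the E2 set can lose a subject because of the outcome it is meant to measure, and no supplied section turns an unmeasurable R-wave at 1 month into a failure.

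The likely effect is small under the planning assumptions. One dropped failure among 141 attendees matters only if true failures number exactly 11, with probability about 4.6% at 95% success and 0.25% at 97%. It matters more if the true rate lies near the 87% goal, where the false-pass chance would move from 1.9% to 4.0% or 7.0% if 1% or 2% of subjects were dropped failures.

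A reader might infer from these figures that the type I error is known to be inflated. It is not: the frequency is not given, and the shares are assumed. The conclusion also rests on all 141 attendees otherwise entering the E2 set, on subjects having met the entry criteria, and on the separate SAP having no rule that settles the matter.

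**What to change.** - In section 12.1.3, count a subject with intrinsic rhythm above 30 bpm and no measurable R-wave at 1 month as 0 mV, that is, an E2 failure.
- Tie the rate criterion of the E2 set to the sensing measurement at a named visit, and reconcile the three cut-offs (above 30, 30 or below, 30 or above).
- In sections 6.5.2.2 and 6.5.3.1, state that the rate for the waiver is established independently of the device's sensing channel, and record this on the CRF.
- Report waived subjects separately. Add a sensitivity analysis that counts every scanned attendee without a 1-month sensing value as a failure.
- If the separate SAP already has such a rule, bring it into section 12.1.3.

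The cost is a few lines of wording and one CRF field. The E2 success rate may come out slightly lower. The sensitivity analysis is deliberately severe, because it also counts subjects whose slow rhythm has nothing to do with the lead; it should therefore stand beside the primary result, not replace it.
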